8.2.1 Infusion/Hypersensitivity Reactions

All biologic therapeutics, including cellular therapeutics, have the potential for causing infusion/hypersensitivity reactions; therefore, these reactions are regarded as class-specific toxicities for biologic therapeutics. Subjects will be closely observed for such reactions during this study. Appropriate facilities for treating infusion/hypersensitivity reactions and individuals trained in the management of such reactions will be immediately available during administration of cePolyTregs. Sites should be instructed to follow their institutional standard operating procedures for the management of infusion/hypersensitivity reactions, should they occur. These treatments may include, but are not limited to, higher doses of corticosteroids, intravenous antihistamines, etc.

8.2.2 Increase in SARS-CoV-2 Viremia, Pneumonia, and Infections Involving Pathogens Not Anticipated in a COVID-19 Setting

All immunomodulatory therapeutics have the potential for causing increased susceptibility to infections; in the present clinical context, this would most likely be manifest as an increase in SARS-CoV-2 viremia or increased incidence of infections including pneumonia or those involving pathogens not anticipated in a COVID-19 setting. Therefore, these reactions are regarded as class-specific toxicities for immunomodulatory therapeutics. Subjects will be closely observed for infections and increases in SARS-CoV-2 viremia during this study.

Enhanced Treg activity may be associated with an increased incidence and/or severity of infections with a variety of extracellular and intracellular pathogens. At the first indication of nascent or active infection, an aggressive diagnostic workup and subsequent antimicrobial therapy will be initiated according to the clinical protocol and local standard of care. As cePolyTregs are expected to be cleared rapidly following administration, it is anticipated that subjects will regain immune competence and clear their infections with appropriate supportive care.

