8.6.2 Secondary Safety Endpoints

Part 1 (Phase 1):

RP2D of cePolyTregs as assessed by cumulative safety, tolerability, pharmacodynamic and biomarker changes associated with administration of cePolyTregs compared with placebo/SOC

Parts 1 and 2:

Safety and tolerability of cePolyTregs as assessed by:

- Type and frequency of TEAEs
- Type and frequency of treatment-emergent serious adverse events (TESAEs)
- Type and frequency of adverse events of special interest (AESIs) including infusion/hypersensitivity reactions, increase in SARS-CoV-2 viremia, and infections including pneumonia and those involving pathogens not anticipated in a COVID-19 setting
- Type and frequency of changes in clinical laboratory values, physical examinations, electrocardiograms (ECGs), and vital signs

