8.8.6 Study Discontinuation

The study may be stopped at the discretion of the Sponsor based on recommendations of the DSMB. The study may also be stopped pending DSMB evaluation of all available safety and PD data if any of the following occur:

- Any study drug-related death
- The occurrence of 3 deaths within 28 days post treatment in the first 5 subjects treated or, subsequent to the first 5 subjects, the observed mortality rate across the cumulative population of treated subjects exceeds the anticipated mortality rate of 50%
- Two CTCAE Grade 4 or 5 TEAEs that are deemed related to study drug
- An increase in the incidence of infections of special interest (pneumonia or infections involving pathogens not anticipated in a COVID-19 setting) beyond the expected background incidence

If the DSMB recommendation is to interrupt study dosing for all subjects or to pause enrollment, study dosing can be resumed, based on the recommendation of the DSMB, only after further review of all available safety data and applicable notifications of submission to appropriate regulatory agencies and institutional review committees, in line with country-specific regulations.

All deaths occurring during the study will be reviewed promptly by the DSMB as they occur. If at any point following enrollment of the first 5 subjects, the observed mortality rate across the cumulative population of treated subjects exceeds the anticipated mortality rate of 50%, the study will be halted.

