12 ADVERSE EVENTS

An AE is defined as any unfavorable and unintended sign (including an abnormal laboratory finding), symptom, or disease or any worsening of a pre-existing condition temporally associated with the use of a study drug, whether or not related to study drug. From signing the ICF to study drug administration, all SAEs and nonserious AEs related to protocol-mandated procedures will be recorded on the SAE/AE eCRF. All other untoward medical occurrences observed during screening, including exacerbation or changes in the medical and surgical history will be captured on the medical and surgical history eCRF.

An AE that occurs before the first administration of the study drug will be considered a pre-treatment AE. A TEAE is defined as any adverse event that was not present before the first administration of the study drug, or any event already present, that worsens in either severity or frequency, following exposure to the study drug. AEs that occur after treatment with IP or during the Safety Follow-up Period will be documented on the AE eCRF. The investigator will assess AE severity, the causality relationship of the AE to study drug, and will treat the subject as medically required to ensure the subject's safety.

AEs will be captured through the EOS Visit at Day 56 or the ET Visit. Reportable adverse events are defined based on timing of study drug administration, as follows:

- Treatment – Day 7: AEs grade 3+ that are not expected to occur in critically ill patients, per the discretion of the investigator.
- Treatment Day 8 – Day84/EOT: AEs grade 4+ that are not expected to occur in critically ill patients, per the discretion of the investigator.

Events expected in the critically ill and are being captured in the eCRF should not be reported as adverse events unless considered to be related to the study drug or unexpectedly severe or frequent per the discretion of the investigator. These include but are not limited to; need for vasoactive drugs or fluids for hypotension, decreased PaO₂/FiO₂, transient hypoxemia, need for renal replacement therapy, or worsening acute respiratory distress syndrome.

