12.2 Adverse Events of Special Interest

To date, there have been no clinical studies using cePolyTregs, and nonclinical studies with autologous, homologous products have not demonstrated specific toxicities related to administration of adoptively transferred Tregs. Potential adverse events of interest in the COVID-19 setting based on the biology of cePolyTregs include infusion/hypersensitivity reactions and infections including pneumonia and those involving pathogens not anticipated in a COVID-19 setting; these clinical parameters will be closely monitored in the current study.

The following events are defined as AESIs that should be reported by completing the Adverse Event eCRF and AESI eCRFs within 24 hours of the site's awareness of them, even if they do not meet criteria for an SAE:

- Evidence of hypersensitivity or transfusion incompatibility (e.g. new rash, urticaria, new onset bronchospasm).
- Diagnostically or clinically confirmed respiratory infections that were not present before study drug infusion AND that require a treatment course with antimicrobial agents, operative management, or procedural drainage.
- Within 6 hours of IP exposure:
 - New ventricular tachycardia, ventricular fibrillation, or asystole or any cardiac arrhythmia requiring cardioversion.
 - Hypoxemia requiring an increase in FiO₂ of 0.2 or more and/or an increase in PEEP of 5 cm H₂O or more to maintain SpO₂ in the target range of 88–95%, for a sustained duration (>2 hours) and not associated with a care procedure.

- Pulmonary Embolism

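### The AESI reporting list in Section 12.2 covers only new, treated respiratory infections, so it is narrower than the AESI endpoint and the infection stopping criterion; viremia also has no scheduled test

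*Combined protocol and SAP*

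**What the plan says.** Section 12.2 opens its list with an operative instruction: "The following events are defined as AESIs that should be reported by completing the Adverse Event eCRF and AESI eCRFs within 24 hours". The one infection entry reads "Diagnostically or clinically confirmed respiratory infections that were not present before study drug infusion", and adds the condition that they need treatment, whether by an antimicrobial course, operative management or procedural drainage. The remaining entries are hypersensitivity or transfusion incompatibility, certain arrhythmias and hypoxemia soon after infusion, and pulmonary embolism.

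Three other places define infections of interest more widely:

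- The AESI endpoint (Synopsis and Section 8.6.2, Parts 1 and 2) includes "increase in SARS-CoV-2 viremia, and infections including pneumonia and those involving pathogens not anticipated in a COVID-19 setting".
- The stopping criterion (Synopsis and Section 8.8.6) is triggered by an increase in "infections of special interest (pneumonia or infections involving pathogens not anticipated in a COVID-19 setting) beyond the expected background incidence".
- The paragraph introducing the 12.2 list names "infections including pneumonia and those involving pathogens not anticipated in a COVID-19 setting; these clinical parameters will be closely monitored in the current study".

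On viremia, Section 8.2.2 states: "Subjects will be closely observed for infections and increases in SARS-CoV-2 viremia during this study".

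General AE reporting is restricted in Section 12. To Day 7 it covers grade 3 or higher events that would not be anticipated in critical illness. From Day 8 to Day 84 it covers "AEs grade 4+ that are not expected to occur in critically ill patients, per the discretion of the investigator". All SAEs are reported within 24 hours whatever their cause (Section 12.6.2).

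**The concern.** Infection is one of the risks that the protocol derives from the biology of this product, and Section 8.2.2 does not confine it to the lung. No clinical study of cePolyTregs precedes this one, so the infection record here is the first. The AESI category exists so that such events are reported even when they are not serious.

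If sites follow the 12.2 list, a bloodstream or urinary infection with an unanticipated pathogen generates no AESI form, although it belongs to the AESI endpoint and to the category that can pause the study. The AESI tables would then describe a narrower set of events than the endpoint they are meant to report. The infection trigger would draw on counts collected under a different definition from its own.

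Viremia raises a separate problem. An endpoint component that nobody measures will show no events, and a reader could take that as reassurance.

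**Working it through.** No sample size, error rate or event rate enters this point, so the check compares the texts.

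**Step 1. Definitions side by side.**

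| Event | AESI endpoint (8.6.2) | Stopping criterion (8.8.6) | 12.2 lead-in | 12.2 reporting list |
|---|---|---|---|---|
| New pneumonia needing treatment | Yes | Yes | Yes | Yes |
| Treated respiratory infection, unanticipated pathogen | Yes | Yes | Yes | Yes |
| Non-respiratory infection, unanticipated pathogen | Yes (no site limit) | Yes (no site limit) | Yes (no site limit) | **No** |
| Increased SARS-CoV-2 viremia | Yes | Not named | Not named | **No** |

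The third row is a contradiction between the list and the three other texts, one of them in the same section. That these texts reach every body site is an inference from the absence of a restriction; none says so expressly. The fourth row is a mismatch with the endpoint only.

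**Step 2. Other routes for a non-respiratory infection with an unanticipated pathogen.**

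| Event | Route to the sponsor | AESI flag and 24-hour AESI form |
|---|---|---|
| Serious, any day | SAE within 24 hours (12.1, 12.6.2) | No |
| Non-serious, grade 3 or higher, to Day 7, unexpected | AE (Section 12) | No |
| Non-serious, grade 4 or higher, Day 8 to Day 84, unexpected | AE (Section 12) | No |
| Non-serious, grade 1 or 2, to Day 7 | No clear route | No |
| Non-serious, grade 1 to 3, Day 8 to Day 84 | No clear route | No |

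Section 12 makes an exception for events common in critical illness: they are reportable if considered related, or if unusually severe or frequent. It is addressed to expected events, does not expressly lift the grade cut-offs, and depends on investigator judgment. The last two rows therefore may go unreported.

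**Step 3. Source of viremia data.** The Schedule of Events lists viral serology for hepatitis B, hepatitis C and HIV. Table 3 lists the same three. Table 4 and Appendix C list SARS-CoV-2 antibody and T-cell responses, but no viral load or viral RNA in blood. No threshold for an increase is given. The component has neither a planned measurement nor a reporting trigger.

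**Step 4. Size.** The documents give no background infection incidence, no split of infections by site and no viremia threshold. The number of events missed cannot be computed.

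**Step 5. Analysis.** Section 13.6 summarizes AESIs by system organ class, preferred term and worst grade, but its cross-reference to their definition is broken. The analysis text does not show whether the 8.6.2 or the 12.2 definition applies.

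**The case against.** A reader might infer that the omitted events go wholly uncounted. The documents do not support that. Every SAE is reported, and the SAE definition includes prolonged hospitalization and important medical events; in subjects who enter on mechanical ventilation, many significant infections could qualify. The threshold for relatedness in Section 12.5 is low. The examples of expected events in Section 12 include no infection, and one with an unanticipated pathogen is hard to call expected. Post-dose antibiotics are recorded (Section 11.14), so a treated infection leaves a trace, although that is not an infection record.

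A reader might also infer that viremia is part of the stopping criterion. It is not; only the endpoint names it.

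A third tempting inference is a demonstrated bias toward apparent safety. In Part 2 the same reporting rules apply to both arms, investigators are blinded, and the primary safety analysis is descriptive, so the contrast between arms need not be distorted. The infection criterion is discretionary and states no background rate or threshold. The DSMB reviews all available data, not only AESI forms. The protocol also refers to a DSMB Charter and a separate SAP, which may hold further detail and are not part of the document.

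These arguments narrow the point. They do not reconcile the 12.2 list with the endpoint. Data that the reporting rules never request are not available to the DSMB.

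**Conclusion.** The inconsistency stands and should be corrected. The AESI list in Section 12.2 is narrower than the endpoint and the stopping criterion for non-respiratory infections with unanticipated pathogens, and narrower than the endpoint for viremia. Every such infection loses the AESI flag and form; only the non-serious ones below the Section 12 grade cut-offs, or judged expected, risk going unreported altogether. Viremia has no data source.

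The omission can only lower the counts; by how much is unknown. Whether the stopping comparison would look too favorable depends on how the background incidence is defined, which the protocol does not say. The conclusion rests on reading the endpoint and the criterion as unrestricted by body site, and on sites treating the 12.2 list as the complete definition, as its introduction indicates.

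**What to change.** 1. Reconcile Section 12.2 with Section 8.6.2, Section 8.8.6 and the Synopsis: add infections with unanticipated pathogens, without restriction to the respiratory tract, to the AESI list and the AESI eCRF. State whether a minimum grade applies, since neither the endpoint nor the criterion sets one. Cost: a short text change, an eCRF update and slightly more site reporting.
2. For viremia, either name a data source (assay, sampling days and what counts as an increase) or remove it from the AESI endpoint, so that zero events are not presented as evidence of safety. Adding it to the 12.2 list alone would produce no data. Removal costs only text, including the matching statement in Section 8.2.2; keeping it costs an assay and a schedule entry.
3. Repair the cross-reference in Section 13.6 so that the AESI summaries point to the reconciled definition. Cost: negligible.

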Safety Analyses: The safety analyses will describe the incidence of adverse events and laboratory abnormalities. All subjects who receive any dose (any amount) of cePolyTregs will be included in the summaries and listings of safety data. Adverse events will be coded according to system organ class and preferred term using MedDRA. AE severity will be graded using the NCI CTCAE. Adverse events will be organized by system organ class and preferred term. Vital signs and physical examination data and change of hematologic and chemistry parameters from baseline will be summarized for each post-baseline visit. Hematologic and chemistry parameters will be categorized as low, normal, or high based on laboratory normal ranges and presented as shifts from baseline.

UCSF	Clinical Study Protocol No. UCSF-cePolyTregs-01	Page 17 of 72
------	---	---------------

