10.4 Study Drug Administration

The cePolyTregs will be infused intravenously into an 18-gauge (or larger) intravenous catheter, either through a peripheral vein (preferred) or central vein. The cells are drawn into a 60 mL syringe via a plasma transfer set and manually infused. A leukoreduction filter must not be used for the infusion.

Emergency medical equipment (i.e., emergency crash cart) must be available during the infusion in case the subject has an allergic response, severe hypotensive crisis, or any other reaction to the infusion. Vital signs (temperature, respiration rate, pulse, SpO₂, and blood pressure) will be

taken before and for a minimum of 30 minutes after infusion and until these signs are satisfactory and stable.

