12.5 Causality Assessment

The investigator or qualified sub-investigator is responsible for assessing and assigning the causality relationship of the event to study drug or study-related procedures (e.g., invasive

UCSF	Clinical Study Protocol No. UCSF-cePolyTregs-01	Page 54 of 72
------	---	---------------

procedures, such as venipuncture) using clinical judgment and the following categories of relatedness:

- Related: There is at least some possibility that the AE could be related to study medication administration.
- Not related: There is a high degree of certainty that the AE is NOT related to study medication administration.

In making a causality assessment of an AE, it should be considered as to whether or not the AE is expected to occur due to the underlying disease, based on the investigator's clinical experience.

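### Section 12.2 has no hypotension item among the AESIs, so intermediate post-infusion hypotension may be recorded unevenly, although a severe crisis would very likely still be reported

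*Combined protocol and SAP*

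**What the plan says.** Sections 10.4 and 10.5 both require emergency equipment to be available during the infusion "in case the subject has an allergic response, severe hypotensive crisis, or any other reaction to the infusion". Section 10.5 is the section on managing infusion/hypersensitivity reactions. The synopsis and section 8.6.2 count those reactions among the AESIs, a secondary safety endpoint in both parts.

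Section 12.2 lists the AESIs that go to the eCRF within 24 hours of the site becoming aware of them, serious or not. Under its 6-hour heading it has "New ventricular tachycardia, ventricular fibrillation, or asystole or any cardiac arrhythmia requiring cardioversion", and hypoxemia that needs an FiO2 rise of at least 0.2 and/or a PEEP rise of at least 5 cm H2O, "for a sustained duration (>2 hours) and not associated with a care procedure". Neither item asks whether the event is related to study drug. A separate hypersensitivity item gives rash, urticaria and bronchospasm as examples. Nothing in section 12.2 mentions hypotension, blood pressure or vasopressors.

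Section 12 says that events expected in the critically ill "should not be reported as adverse events unless considered to be related to the study drug or unexpectedly severe or frequent", at the investigator's discretion. The first example is "need for vasoactive drugs or fluids for hypotension".

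Section 12.5 defines an event as related when "There is at least some possibility that the AE could be related to study medication administration", and reserves the unrelated category for cases of high certainty. It then adds that "it should be considered as to whether or not the AE is expected to occur due to the underlying disease".

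**The concern.** The protocol names an acute reaction in the infusion sections, makes infusion reactions an endpoint, and then gives that reaction no explicit place in the list that puts the endpoint into practice. The general AE rule works in the opposite direction, because hypotension treated with vasoactive drugs is by default not an AE. Whether it reaches the form depends on the investigator's opinion about cause, or about unexpected severity or frequency.

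All subjects are ventilated ARDS patients at entry, so hypotension has a ready alternative explanation. Section 12.2 states that cePolyTregs has not been studied clinically before. At stake is whether the descriptive AESI and TEAE tables, built from up to 12 centers, count post-infusion hypotension by one rule or by each investigator's habit. An event screened out as expected leaves no AE entry, and so no causality assignment that the sponsor or DSMB could look at again.

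**Working it through.** The plan has no figure to reproduce on this point. The check sets the sections side by side.

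**1. Is hypotension in the AESI list?** The two items clearly under the 6-hour heading are arrhythmia and sustained hypoxemia. The other items are hypersensitivity or transfusion incompatibility, respiratory infection and pulmonary embolism. Items for hypotension or vasopressor use: none.

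**2. Is the contrast with hypoxemia fair?** In part. The expected-event list in section 12 includes decreased PaO2/FiO2 and transient hypoxemia. The 12.2 hypoxemia item asks for more than 2 hours, so it does not overlap with the transient kind. It does overlap with decreased PaO2/FiO2, and there section 12.2 supplies an objective trigger despite the expected-event list. Arrhythmia is not named on that list. The care-procedure clause in the hypoxemia item is a judgement, but not one about study drug.

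**3. By which routes can post-infusion hypotension reach an event form?**

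- *Hypersensitivity AESI.* The examples are open-ended, but someone must first see the hypotension as hypersensitivity or incompatibility.
- *AE, related.* The bar in section 12.5 is low, but the same section asks the investigator to weigh what the underlying disease would produce.
- *AE, unexpectedly severe or frequent.* A severe crisis would usually qualify. A modest new vasopressor need may not.
- *SAE.* Section 12.6.2 requires a 24-hour report whatever the cause. The event must first count as an AE and then meet a seriousness criterion.

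A severe crisis passes several of these routes. A new vasopressor start of ordinary size that the investigator puts down to ARDS may pass none.

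**4. What is captured outside the event forms?** Section 11.14 collects vasopressors, and changes in blood pressure medication, after dosing. Section 10.4 continues vital signs after infusion until they are satisfactory and stable. The synopsis says "Vital signs and physical examination data and change of hematologic and chemistry parameters from baseline will be summarized for each post-baseline visit". The WHO scale is scored daily in hospital, although a subject already on pressors is in category 7 and cannot move higher except by dying. These data exist, but none of them starts a 24-hour AESI report or enters the AESI count.

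**5. Which endpoints are touched?** The DLT definition and the Part 2 primary safety endpoint both count only related events of grade 3 or higher. A trigger that ignores causality changes neither directly.

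**6. What would a new trigger add as background?** The documents give no rate. Assume, for illustration only, that 10% to 40% of infused subjects would meet it with an inert product:

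- All subjects: 118 × 0.10 = 11.8 and 118 × 0.40 = 47.2, so about 12 to 47 reports.
- Part 1, up to 18 subjects: 1.8 to 7.2.
- Part 2, per arm of 50: 5 to 20.
- At least one among the 6 subjects at the RP2D: 1 − 0.9^6 = 0.469 and 1 − 0.6^6 = 0.953.

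**The case against.** The strongest reply is that the protocol already covers the event it names. Severe hypotensive crisis appears in the section on infusion/hypersensitivity reactions, those reactions are AESIs by endpoint definition, and the examples in section 12.2 are not exhaustive. Such a crisis would also normally count as unexpectedly severe. It could be an SAE reportable regardless of cause, and it would be hard to call unrelated when that needs a high degree of certainty. Section 11.14 separately targets changes in blood pressure medication. Which ICU events get an automatic trigger is partly the sponsor's judgement.

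Most of this stands. A reader might infer that a severe crisis could go unreported, and the documents do not support that. A reader might also point to the interval between the post-infusion vital signs and the next scheduled assessment. That is not a reporting gap, because AESI reporting runs from site awareness, and the arrhythmia and hypoxemia items work under the same schedule.

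The reply does not cover the intermediate event. There the related route, the unexpectedly-severe route and the hypersensitivity item each turn on individual judgement, and section 12 sets the default at not reporting.

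**Conclusion.** The point holds in a limited form. Section 12.2 only partly puts the infusion/hypersensitivity AESI endpoint into operation, and the likely result is non-uniform recording of intermediate post-infusion hypotension. The amount cannot be estimated, because the documents give neither hypotension rates nor reporting rates.

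Two further inferences should be resisted. One is that DLTs are undercounted through this gap: DLTs require relatedness, so the missing trigger has no direct effect on them. The other is bias between arms in Part 2: the judgements belong to investigators, who are blinded, so the expected result is fewer recorded events in both arms. That second conclusion assumes the investigator blind holds, since sections 10.2 and 10.7 leave other site staff unblinded.

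This is a cheap improvement to safety recording. It is not a flaw that threatens the trial's conclusions.

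**What to change.** 1. In the section 12.2 hypersensitivity item, add hypotension to the examples.
2. In section 12.2, under the 6-hour heading, add: *Hypotension requiring start of a vasopressor, or addition of another vasopressor agent, not associated with a care procedure*, reported regardless of causality.
3. In section 12, state that the expected-event list does not override section 12.2.

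Starting or adding an agent is observable without a dose threshold. The documents give no basis for choosing such a threshold, and a minimum-duration rule would miss a crisis reversed quickly. An increase in the dose of an agent already running, or hypotension treated with fluids alone, stays outside item 2. It is still reportable through the hypersensitivity item, or as a related or unexpectedly severe event.

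The cost is a few words in section 12.2, one sentence in section 12 and one eCRF option. The downside is that some background ICU hypotension will be reported as AESIs, at a rate the documents do not give. Part 1 counts should therefore not be read as drug effect. Under the assumed 10% to 40%, an inert product would show at least one such event among the 6 RP2D subjects with probability 47% to 95%. Part 2 counts should be compared with placebo.
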